**VII.E.7**      **Will you attempt to recontact subjects who are lost to follow-up?**  
No - followup is not required in this study

**VII.E.9**      **Will subjects be provided any compensation for participating in this study?**  
No

## VIII. Risks

### VIII.1

**What are the risks to subjects including**

- emotional or psychological
- financial
- legal or social
- physical?

There may be risks associated with being in this study. You may experience pain and bruising at the insertion site of the IV line. There is also a low risk of infection at this site. These risks are associated with the surgical procedure and not the research.

There is the potential that your confidentiality could be breached and persons not on the research team could learn about your study participation, but we will safeguard your data as described in the confidentiality section. There may be unforeseen risks associated with participation in this research.

### VIII.2

**What have you done to minimize the risks?**

- **If applicable to this study ALSO include:**
  - How you (members of your research team at Iowa) will monitor the safety of individual subjects.
  - Include a description of the availability of medical or psychological resources that subjects might require as a consequence of participating in this research and how referral will occur if necessary (e.g. availability of emergency medical care, psychological counseling, etc.)

There are no risks to this study. The intravenous catheter will be placed by an oral and maxillofacial surgery faculty or resident, so the patient will be monitored by that surgeon during intravenous placement (as are all patients).

### VIII.3

**Does this study have a plan to have an individual or committee review combined data from all subjects on a periodic basis (such as summary or aggregate safety and/or efficacy data)?**

No

## IX. Benefits

### IX.1

**What are the direct benefits to the subject (do not include compensation or hypothesized results)?**

No direct benefits

### IX.2

**What are the potential benefits to society in terms of knowledge to be gained as a result of this project?**

Decreased anxiety and fear in seeking treatment with IV sedation. Help decrease needle phobias and/or pain related to IV insertion, vaccinations, etc. This could help other oral and maxillofacial surgery clinics, and other organizations, such as blood banks, in seeking adult participants.

## X. Privacy & Confidentiality

### X.1

**What are you doing to protect the privacy interests of the subjects?**

The questionnaire form that will be collected will only contain the record number in order to track device usage as required by the IRB proposal. All forms will be kept secured in a locked file and stored by the PI. Only data which is related to the study will be collected. The minimum amount of private information needed to answer the research question will be collected.

### X.2

**Are you collecting the Social Security Number of any subjects for any purpose?**

No

### X.4

**How will information/data be collected and stored for this study (check all that apply):**

- Paper/hard copy records (hard copy surveys, questionnaires, case report forms, pictures, etc.) - A file will be kept by the PI with the paper records as noted above. The files will be stored in a room that is locked when not in use. The patient's name will not appear on the record, instead only their record number will be used.
- Electronic records (computer files, electronic databases, etc.) - After collection of the paper records and sufficient data, the data will be put into an electronic format for data analysis. The data will be stored and accessed on University of Iowa Hospitals and Clinics and College of Dentistry computers. These computers are password protected with UIHC healthcare logon identification.
  - Name - [name]
  - Title - Associate Vice President, Healthcare Information Systems
  - University Job Classification - Staff

### X.5

**Do the confidentiality protections indicated above allow only members of the research team to access the data/specimens?**

Yes

**X.7** **Does your study meet the NIH criteria for a [Certificate of Confidentiality](#) or will you be applying for [Certificate of Confidentiality](#)?**  
No

## XI. Data Analysis

**XI.1** **Describe the analysis methods you will use, including, if applicable, the variables you will analyze**  
Simple descriptive statistics would be used to summarize the data. Normality of data will be assessed by Kolmogirov Smirnov test. Continuous outcomes would be assessed by t-tests, ANOVA, and multivariable linear regression models. Categorical variables would be assessed by Chi-square tests and multivariable logistic regression models. All tests will be two sided and a p-value of <0.05 would be set for statistical significance.

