**I.3** **Short Title (optional):**

**I.4** **Provide a short summary of the purpose and procedures of the study proposed in this IRB application.**

- **DO NOT include information on studies not proposed in this application.**
- **Use LAY terminology only. This must be easily understandable by IRB community members and nonscientists.**
- **DO NOT cut and paste technical abstracts from funding applications that may not be understood by a general audience.**

A large number of dentoalveolar (tooth extraction) procedures performed by Oral and Maxillofacial Surgeons utilize intravenous sedation. Procedures commonly performed may include surgical removal of teeth, bone grafting, surgical placement of dental implants, and removal of cysts or tumors from the jaws, among others. Obtaining peripheral intravenous (IV) cannulation often proves to be a very stressful and anxious event for the patient. The anxiety and stress from the venipuncture alone affects not only the psychological stability of the patient, but also the patient's physiology. The Buzzy vibration external stimulation device has shown to be an effective tool in pediatric venipuncture procedures. The aim of this study is to investigate the effects of the Buzzy stimulation device in pain and anxiety reduction during peripheral intravenous cannulation in an adult population.

Enrollees in this study will be patients who will undergo dental surgery with intravenous sedation. The patients who are enrolled will receive an IV either with or without the Buzzy. The Buzzy is a small vibration device which will be placed next to the IV placement site.

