**I.5** **Specify your research question(s), study aims or hypotheses (do not indicate "see protocol")**

- To investigate the efficacy of the Buzzy stimulation device in pain and anxiety reduction during peripheral intravenous cannulation in an adult population.
- Determine any benefit of the Buzzy system between men and women.
- Determine any benefit of the Buzzy system between different age ranges in adults.
- Is there a site benefit with the Buzzy system?

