**XI.2** **Provide the rationale or power analysis to support the number of subjects proposed to complete this study.**  
Population mean = 3.42 points (std.dev of 3.10) [Wong-Baker FACES scale score]  
Expected clinical difference to be detected = 2 point differences in Wong-Baker FACES scale score  
Alpha = 0.05  
Power = 80%  
Sample size required is 38 patients in each of control and intervention groups (total sample size is 76 patients).  
To allow for better statistical analysis and for patients excluded due to missed IV access attempts, etc. up to 100 patients may be enrolled.

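### Pain and anxiety share one efficacy aim and each is tested at p<0.05 with no order or adjustment; if either can carry the claim, its false-positive rate is about 7–10%, not 5%

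*Combined protocol and SAP*

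**What the plan says.** Section XI.1 is the whole analysis plan; VII.B.11 confirms that no separate protocol exists. Its decision rule is "All tests will be two sided and a p-value of <0.05 would be set for statistical significance". For continuous outcomes it lists several methods: "Continuous outcomes would be assessed by t-tests, ANOVA, and multivariable linear regression models". It does not assign a method to an outcome.

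The efficacy aim in I.5 names two outcomes together: "To investigate the efficacy of the Buzzy stimulation device in pain and anxiety reduction". The lay summary in I.4 says the same. I.5 then adds questions on sex ("Determine any benefit of the Buzzy system between men and women"), age range and insertion site.

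The sample size in XI.2 rests on one comparison: "Expected clinical difference to be detected = 2 point differences in Wong-Baker FACES scale score", with alpha 0.05 and 80% power, giving "Sample size required is 38 patients in each of control and intervention groups". XI.2 does not call this score primary. It does not label it as pain either, although that is the natural inference.

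**The concern.** The plan offers two routes to a positive efficacy finding, each at the full 5% level. Anxiety is not a side issue: I.4 motivates the study partly by the anxiety of venipuncture, and IX.2 puts reduced anxiety and fear first among the benefits to society. A trial with a significant anxiety result and a null pain result could therefore be reported as showing efficacy, and nothing in the plan says whether that would be legitimate. If it is, the claim carries a larger chance of being false than the stated 0.05 suggests. No one has to pick the smaller p-value for this to happen; it follows from applying the written rule to both outcomes.

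**Working it through.** **Inputs from the documents.** Two-sided 0.05 for every test (XI.1). Difference of 2 points, SD 3.10, alpha 0.05, power 80%, 38 per arm, up to 100 enrolled (XI.2). Allocation 1:1 (VII.E.2). Two outcomes in the efficacy aim (I.5).

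**Input assumed.** The correlation r between the pain and anxiety test statistics. The documents give no value, so a range of 0 to 0.9 is shown.

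**1. The plan's own figure.** n per arm = 2 × [(1.960 + 0.842) × 3.10 / 2]² = 37.7, which rounds up to 38. The stated figure reproduces as a two-sided, single-outcome calculation by normal approximation. Solving with the t distribution gives 38.7, so 39. Power by noncentral t is 79.3% at 38 per arm and 89.1% at 50 per arm.

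**2. One outcome.** With no true effect, the FACES comparison alone is significant 5% of the time. Nothing below changes that.

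**3. Either of two outcomes.** With no effect on either, P(at least one significant) = 1 − P(|Z₁| ≤ 1.96 and |Z₂| ≤ 1.96). For r = 0 this is 1 − 0.95² = 0.0975. For other r it comes from the bivariate normal distribution:

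| r (assumed) | at least one significant |
|---|---|
| 0 | 9.75% |
| 0.3 | 9.5% |
| 0.5 | 9.1% |
| 0.7 | 8.3% |
| 0.8 | 7.8% |
| 0.9 | 7.0% |

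Whatever the correlation, two tests cannot exceed 0.05 + 0.05 = 10%.

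**4. Both outcomes required.** P(both significant) = 0.05 + 0.05 − P(at least one). This is 0.25% at r = 0 and 0.10 − 0.0704 = 3.0% at r = 0.9. Under this reading there is no inflation when neither outcome has an effect.

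**5. Fixed sequence, FACES first.** Anxiety can be declared significant only after FACES is. With no effect on FACES, any false claim needs a false-positive FACES result, so the rate is at most 5%. With a real FACES effect, the only possible false claim is on anxiety, again at most 5%. FACES is still tested at 0.05, so its power stays at 79.3% (38 per arm) or 89.1% (50 per arm). The gate stays closed in 100 − 79.3 = 20.7% of trials at 38 per arm when the 2-point effect is real, and in 10.9% at 50 per arm.

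**6. Alpha split, for comparison.** At 0.025 for each outcome, FACES power falls to about 70% at 38 per arm, and 80% needs 47 per arm by t-test.

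**The case against.** The strongest objection is that the inflation depends on a decision rule the documents do not contain. If pain and anxiety are two separate claims, each keeps its own 5%. If both must succeed, step 4 shows no inflation. This stands, and it is why the 7–10% figure is conditional. It does not remove the point, because the plan gives no means of telling which reading applies.

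A reader might infer a rate of up to about 14%, since XI.1 lists regression beside t-tests. Reaching that level takes both an unadjusted and an adjusted test of each outcome, all used to claim significance, and a covariate assumed to correlate about 0.5 with the outcomes. XI.1 lists types of method; it does not say that each arm effect is tested twice, and it names no covariate. The regression may be meant for the sex, age and site questions. The plan does not rule out double testing, but it does not state it.

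A reader might also infer that the sample-size alpha is wrong. It is not: the 0.05 in XI.2 belongs to one comparison, and that comparison runs at 5%.

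The questionnaire is not in the documents. The timing of the FACES score and the form of the anxiety item are unknown. If anxiety is categorical, XI.1 would send it to a chi-square test or logistic regression. The 10% ceiling holds for any two valid 0.05-level tests, but the exact values in the table rest on approximate normality of both statistics.

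Finally, the choice of test is open. One prespecified adjusted test would hold 5% as well as the unadjusted t-test does. If a baseline covariate correlated 0.5 with the score, the residual SD would be 3.10 × √0.75 = 2.68 and power at 38 per arm about 89% rather than 79%. Insisting on the unadjusted test would be a preference.

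**Conclusion.** The point holds in conditional form. The plan applies p<0.05 to two outcomes under one efficacy aim, with no primary outcome, order or adjustment. If either outcome alone may support the claim, its false-positive rate with no true effect is about 7–10% for correlations from 0.9 down to 0, and never above 10%. The FACES comparison itself is sound and correctly sized by normal approximation. The conclusion assumes that FACES is the pain score, which XI.2 implies but does not say, and takes the correlation over a range because no value is given. It is a moderate matter: the sized comparison stays valid, but the error rate for the efficacy aim as worded is not controlled, and the remedy is cheap.

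**What to change.** Before data are examined, add to XI.1:

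1. The primary comparison is the between-arm difference in the Wong-Baker FACES score on which XI.2 is sized, stating that it is the pain score (if so) and when it is recorded. It is tested by one prespecified method at two-sided 0.05 and reported with a 95% CI. Whether that method is unadjusted or adjusted for a named covariate is for the investigators to choose, once.
2. The between-arm difference in anxiety, on a named item, is tested at two-sided 0.05 only if the primary test is significant. Otherwise it is reported as an estimate with a 95% CI.
3. Any other model for the same outcome is a sensitivity analysis and carries no separate significance claim.
4. The sex, age and site questions are exploratory and reported as estimates with 95% CIs.

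This takes a few sentences, with no extra patients, no new data and no loss of FACES power. The price is that anxiety cannot be claimed as confirmed when the FACES test misses: about 21% of trials at 38 per arm and 11% at 50 per arm under the full 2-point effect, and more if the effect is smaller. If the investigators regard anxiety as equally important, an alpha-sharing procedure such as Holm would also control the error, but FACES would no longer be guaranteed the full 0.05.

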**XI.2** **Provide the rationale or power analysis to support the number of subjects proposed to complete this study.**  
Population mean = 3.42 points (std.dev of 3.10) [Wong-Baker FACES scale score]  
Expected clinical difference to be detected = 2 point differences in Wong-Baker FACES scale score  
Alpha = 0.05  
Power = 80%  
Sample size required is 38 patients in each of control and intervention groups (total sample size is 76 patients).  
To allow for better statistical analysis and for patients excluded due to missed IV access attempts, etc. up to 100 patients may be enrolled.

## XII. Future Research

**XII.1** **Do you wish to keep any information about subjects involved with this research project so that members of the current research team may contact them in the future for your own research projects?**  
No

**XII.2** **Do you wish to keep any information about subjects involved with this research project so that [other researchers](#) may contact them for future research?**  
No

**XII.4** **Does this project involve storing any data, tissues or specimens for future research?**  
No
